3.2.3 Study Definitions

Clinical Residual Defect Status – categories defined based on clinical characteristics of the residual shunt at study follow-up intervals as determined by the echocardiography core lab:

1. **Completely Occluded**, defined as absence of residual shunt
2. **Clinically Insignificant Residual Shunt**, defined as all of the following:
 - a. Residual shunt is hemodynamically insignificant based on any of the following characteristics:
 - i. Normalization of ventricular septal motion
 - ii. Significant decrease in right ventricular size as determined by comparison of equivalent parasternal and apical images of the right ventricle pre- and post-device placement
 - b. No clinical sequelae related to the leak
3. **Clinically Significant Residual Shunt**, defined as any of the following:
 - a. A residual left to right shunt or right heart volume overload that would likely require repeat intervention
 - b. Clinical sequelae related to the leak
 - c. Hemodynamically significant, defined as failure to meet criteria for hemodynamically insignificant detailed above

Measured Residual Defect Status – If present, residual defect size should be measured at post-implant, pre-discharge and all subsequent follow up evaluations. During the Core Lab analysis, the categories will be defined based on measured size of the target ASD residual shunt and compared to the guideline below:

1. Occluded = absence of residual shunt
2. Trivial = >0 to ≤ 2 mm residual shunt

CONFIDENTIAL INFORMATION

3. Moderate = >2 to ≤ 4 mm residual shunt
4. Large = >4 mm residual shunt

4.0 Description of Population

Subjects with an *ostium secundum* ASD having a stop flow balloon diameter of less than or equal to 17 mm may be enrolled. Baseline variables are assessed by means of physical examination, electrocardiogram (ECG), and transthoracic or transesophageal echocardiography (TTE or TEE).

Subjects with additional cardiac conditions requiring surgery at the time of ASD closure or anticipated within three (3) years of enrollment are not permitted in the study due to possible confounding adverse events. Overall health, age and other underlying conditions should be considered prior to patient enrollment.

Only patients who meet all of the Inclusion Criteria and none of the Exclusion Criteria will be enrolled.

4.1 Inclusion Criteria

All responses must be Yes to be eligible.

1. Patient has an *ostium secundum* ASD with evidence of right ventricular volume overload.
2. Patient has a defect size of ≤ 17 mm as measured directly by stop flow balloon sizing.
3. Patient vasculature is able to accommodate the delivery system and/or procedural accessories.
4. Patient is able to accommodate TEE or ICE probe for implant procedure.
5. Patient is judged to have adequate septal rims to retain the device.
6. Patient (or legal guardian, if subject is a minor) must voluntarily sign a Patient Informed Consent Form specific to the study. The Patient Informed Consent Form must be reviewed and approved in a manner that complies with requirements of the hospital's Institutional Review Board.
7. Patient (and legal guardian, if patient is a minor) must be physically and mentally willing to comply with all study follow-up

CONFIDENTIAL INFORMATION

requirements through 36 months, including routinely scheduled diagnostic testing and physical examinations.

4.2 Exclusion Criteria

All responses must be *No* to be eligible.

[figure not shown]
1. Patient has significant known pre-existing electrophysiologic, structural cardiovascular defect, or other comorbidities that could elevate morbidity/mortality beyond what is common for ASD or that is expected to require surgical treatment within three (3) years of device placement. Examples include but are not limited to: large ventricular septal defect, hypoplastic left heart syndrome, coarctation, univentricular heart or tricuspid atresia, arrhythmias requiring electrophysiology study, or intervention concurrent with device placement.
2. Patient has systemic or inherited conditions that would significantly increase subject risk of major morbidity and mortality during the term of the study. Examples would be endocarditis, cancer, degenerative neuromuscular disorder, cardiomyopathy, or any condition expected to result in significant deterioration of health within three (3) years of the index procedure.
3. Patient has anatomy where the size or position of the occluder would interfere in other intracardiac or intravasculature structures, such as cardiac valves or pulmonary veins.
4. Patient has active endocarditis, other infections producing bacteremia, or has known sepsis within one month of planned implantation, or any other infection that cannot be treated successfully prior to device placement.
5. Patient has one (or more) known intracardiac thrombi.
6. Patient has an uncontrolled arrhythmia.
7. Patient has a history of stroke resulting in a significant morbidity or disability.
8. Patient is pregnant or lactating at time of enrollment.
9. Patient has contraindication to antiplatelet therapy.
10. Patient has a pulmonary artery systolic pressure greater than half the systemic systolic arterial pressure unless the indexed pulmonary arteriolar resistance is <5 Woods units.
11. Patient has multiple defects based on screening imaging and stop flow balloon sizing that would require placement of >1 device.

CONFIDENTIAL INFORMATION

5.0 Study Procedures and Evaluations

5.1 Study Evaluations Schema

CONFIDENTIAL INFORMATION

5.2 Schedule of Events

The table below presents the procedures and evaluations for each protocol interval.

Procedure / Evaluation	Screening / Pre-procedure (within 6 mo of index procedure)	Procedure	Pre-discharge	Unsuccessful Implant – 30 Days (day 30; \pm 14 days)	30 Days (day 30; \pm 14 days)	6 Months (day 180; \pm 14 days)	12 Months (day 365 \pm 60 days)	24 Months (day 730; \pm 60 days)	36 Months (day 1095 \pm 60 days)
Screening Evaluation and estimated defect size* (TTE, TEE or ICE)	X								
Patient Informed Consent & HIPAA	X								
Demographics and Medical History	X								
Physical Exam	X	X			X	X	X		X
TTE/TEE/ICE (subcostal, parasternal, and apical 4-chamber views)		X	X		X	X	X		X
ECG	X		X		X	X	X		X
Antiplatelet Therapy		X	X		X	X			
Telephone Questionnaire				X				X	
Assess Adverse Events		X	X	X	X	X	X	X	X
Fluoroscopy (without contrast; Enface and lateral views)**						X**			X**

* performed within 6 months prior to index procedure

** Only if clinically indicated for certain subjects. Refer to Section 5.4.8 for details

CONFIDENTIAL INFORMATION

5.3 Informed Consent Process

All patients must provide informed consent, or assent for minors, prior to any study related procedures being performed. The case history (i.e. source documents/subject chart) for each subject must document that such informed consent was obtained. The patient, and authorized representative when applicable, must sign and date the informed consent form (ICF). The Investigator or designee must also sign the ICF. The patient will be provided with a copy of the signed and dated ICF and the original will be maintained at the Investigator site.

5.4 Screening/Pre-treatment, Enrollment, Procedure, and Follow-up

In all cases, the Investigator maintains exclusive responsibility for the inclusion and exclusion of any potential study participant(s). All patients presenting for treatment of ASD are evaluated for study participation based on the inclusion/exclusion criteria provided in this protocol.

5.4.1 Screening /Pre-treatment Evaluation

When the Investigator identifies a patient as a potential candidate for inclusion in the study, the necessary medical history, physical exam and inclusion/exclusion criteria are reviewed. If the patient meets the criteria for entry into the study, the *Patient Informed Consent Form* is administered.

A screening evaluation is performed within six (6) months of procedure to identify initial suitability of defect closure. This pre-treatment patient evaluation will assess eligibility variables by means of physical examination, electrocardiogram (ECG) and transthoracic echocardiography (TTE), transesophageal echocardiography (TEE) or other appropriate imaging to estimate static defect size of 17 mm or less may be enrolled. Peri-procedural antibiotics may be prescribed at the discretion of the Investigator.

Subjects with additional cardiac conditions anticipated to require surgery within three (3) years of enrollment are not permitted in the study. In addition, no concurrent intervention(s) should be performed during the occluder procedure.

5.4.2 Screen Failure

Patients who consent to participate in the study, but who are determined to not have suitable anatomy and no GORE® Septal Occluder implant or placement is attempted, will be considered screen failures and will not be followed in this study (see Study Schema, Section 5.1). No post-procedure study follow-up or contact will be required for these

CONFIDENTIAL INFORMATION

patients. Screen failures will be recorded on the appropriate case report form (CRF) in the EDC system.

5.4.3 Enrollment

A subject is considered enrolled into the clinical study when the GORE® Septal Occluder device is introduced into the anatomy of the subject. Subjects who enroll in the trial and have a successful implant should be followed through 36 months post index procedure (see Study Schema, Section 5.1).

5.4.4 Transcatheter Procedure

Subjects will be consented to the GORE® Septal Occluder Study prior to transcatheter procedure.

Subjects will undergo placement of the GORE® Septal Occluder via a transcatheter procedure. During the transcatheter procedure either transesophageal echocardiography (TEE) or intracardiac echocardiography (ICE) will be performed with general anesthesia or conscious sedation based on the institution or Investigator's general practice. These are acceptable testing modalities during the transcatheter procedure. Procedure time begins upon venous cannulation and procedure time ends upon removal of the final catheter.

At that time, under general anesthesia or conscious sedation and by utilizing transesophageal echocardiography (TEE) or intracardiac echocardiography (ICE), either TEE or ICE static sizing and stop flow balloon sizing of the defect takes place. Static and stop flow balloon defect sizing of 17 mm or less and cardiac anatomy will determine final patient suitability and the appropriate device size for closure of the defect.

Data will be recorded to characterize the procedure.

5.4.4.1 Recommended Procedure Technique (Instructions for Use)

Detailed Instructions for Use for placement of the GORE® Septal Occluder may be found in the GORE® Septal Occluder package as well as in Study Regulatory Binder.

The following recommendations should be considered when choosing the appropriate GORE® Septal Occluder for the subject:

1. The selected occluder nominal diameter should be in a range reflecting 1.75 times the stop flow diameter of the defect (1.75:1 ratio of device nominal diameter-to-defect diameter).
2. The defect should be evaluated to ensure there are adequate septal rims to retain the device.

CONFIDENTIAL INFORMATION

3. The occluder size and position should be evaluated to ensure no interference with other intracardiac or intravascular structures, such as cardiac valves or pulmonary veins.
4. If successful deployment cannot be achieved after three (3) attempts, an alternative treatment for ASD closure is recommended. Consideration should be given to the patient's total exposure to radiation if prolonged or multiple attempts are required for placement of the occluder.
5. Removal of the occluder should be considered if:
 - Lock loop does not capture all three eyelets;
 - Occluder will not come to rest in a planar position apposing the septal tissue;
 - Occluder allows excessive shunting; or
 - Impingement on adjacent cardiac structures is observed.

Expansion of an occluder disc may occur in the periprocedural time period. If there is uncertainty that an expanded device remains locked, fluoroscopic examination without contrast is recommended in order to identify if the Lock Loop captures all three eyelets.

5.4.4.2 *Access Site Management*

Closure of the femoral venous puncture site should be performed per hospital standards. Access site hemostasis may be achieved by manual compression, or by utilizing alternative methods, such as a suture closure device.

5.4.5 *Pre-Discharge*

Prior to institutional discharge, pre-discharge evaluations will be performed following the schedule of events (section 5.2). Imaging required is either transesophageal or transthoracic echocardiography (TEE/TTE) or intracardiac echocardiography (ICE).

5.4.6 *Unsuccessful GORE® Septal Occluder Procedure*

Subjects with unsuccessful placement of a GORE® Septal Occluder (no study device implanted at conclusion of index procedure) will be followed through 30 days post index procedure. Subjects will be contacted by phone at 30 days for follow-up; upon completion of the telephone follow-up Case Report Form (CRF) at the 30-day Unsuccessful Implant interval, subject is discontinued from the study. These subjects will be considered enrolled and a technical failure for purposes of study analysis.

CONFIDENTIAL INFORMATION

5.4.7 Post-Procedure Care

At the discretion of the Investigator, subjects will be encouraged to limit their physical activities for at least two weeks after occluder placement. In uncomplicated cases with satisfactory closure, subjects may be discharged from the hospital as soon as deemed appropriate by the study Investigator.

Patients are required to be treated with antiplatelet therapy, such as aspirin and/or clopidogrel bisulfate, for 6 months post index procedure per the institutional standard of care or physician's general practice. The decision to continue antiplatelet therapy beyond 6 months is at the discretion of the Investigator.

5.4.8 Post-Procedure Evaluations and Testing

Post-procedure evaluations will be performed according to the schedule of events. Follow-up information will be recorded in the Clinical Data Management System (CDMS) through the 36 month interval or at the time of subject withdrawal or discontinuation from the study.

At post-procedure follow-up intervals (30 days, 6, 12, and 36 months) a TTE or TEE is required for all subjects with the GORE® Septal Occluder to evaluate defect closure status.

Fluoroscopic examination without contrast (En face and lateral views) will be performed at the 6 and 36 month intervals in order to identify and assess wire frame fractures. Please refer to the requirements below to determine if fluoroscopic evaluation is required for subject, or only necessary if clinically indicated.

Lack of device stability may be indicative of wire frame fractures. All device fractures are reported on the Subject Follow-up Evaluation CRF. Additionally, device fractures that result in device removal because of device instability or other clinical sequelae will be reported as adverse events. Chest x-ray is not suitable imaging to evaluate the occluder and defect closure.

Fluoroscopy Requirements

- Subject IDs referenced with 100 and 200 numbers within the study database must complete 6 and 36 month fluoroscopic imaging. These are the first 150 subjects enrolled (50 Pivotal and 100 Continued Access).
- Subject IDs with 300 numbers, fluoroscopic images are optional and only recommended in subjects where device stability is questionable at any follow up interval. Subjects

CONFIDENTIAL INFORMATION

enrolled with 300 numbers begin with the 151st enrollment through the time of PMA approval.

Institutional subject records or documents from a referring institution or physician (i.e., catheterization report, discharge summary, or echocardiographic transcription) should not be forwarded to the Sponsor. Necessary records should be available for scheduled monitoring by the Contract Research Organization (CRO) on the Sponsor's behalf. Documentation for adverse events may be requested.

All echocardiography and fluoroscopy images obtained at procedural and study follow up intervals must be recorded in DICOM format according to echocardiographic guidelines provided with this protocol and uploaded to the BioClinica WebSend secure web portal. Baseline and implant images will be reviewed by the Echo Core Lab to assist in evaluating closure progress at subsequent intervals.

At the 24 month interval subjects should be contacted and a telephone questionnaire CRF completed.

All planned and unplanned visits, regardless of etiology, will be documented in the CDMS system, including reporting of any adverse events. It is important that the Investigator encourage subjects to return for all required follow-up visits. The clinical study objectives will not be realized if a significant number of subjects are lost to follow-up or discontinued from further study participation.

5.4.9 Reinterventions

Reinterventions to the study device (GORE® Septal Occluder) will be reported on the Intervention CRF. If the GORE® Septal Occluder is removed as part of the reintervention, then the subject is discontinued from the study. If the GORE® Septal Occluder remains implanted, then the subject will continue to be enrolled and will complete study follow-up as prescribed.

5.4.10 Follow-up Visit Windows

The follow-up visits should be completed within an acceptable time frame and in accordance with the protocol defined visit windows. The follow-up intervals are calculated as calendar days from index procedure. The visit windows are calculated as +/- the number of calendar days.

30 Days	6 Months	12 Months	24 Months	36 Months
Day 30 +/- 14 days	Day 180 +/- 14 days	Day 365 +/- 60 days	Day 730 +/- 60 days	Day 1095 +/- 60 days

CONFIDENTIAL INFORMATION

If the visit is not able to be completed during these windows the visit should be completed as soon as possible; however, it will be considered a protocol deviation and should be reported per local Institutional Review Board (IRB) policy. Visits performed outside the prescribed window will be reported as an Unscheduled visit.

5.5 Subject Withdrawal from the Clinical Study

A subject may withdraw from the clinical study at any time and for any reason, and should notify the Investigator in this event. Subjects are not obligated to reveal their reasons for withdrawal. The subject will be withdrawn if he/she relocates to another geographic area that requires a change of physician and such suitable physician cannot be identified.

The Investigator may withdraw the subject from the clinical study at any time based on his/her medical judgment. It is important that the Investigator encourage subjects to return for all required follow-up visits within the designated window. The clinical study objectives may not be realized if a significant number of subjects are lost to follow-up. A subject may withdraw, or be withdrawn by the Investigator, if he or she is unable to continue participation in the study due to any condition unrelated to the study.

The Investigator or designee must complete the appropriate CRF (Study Completion/Discontinuation Form) documenting the subject's withdrawal or discontinuation from the clinical study. The subject will be considered withdrawn once the Sponsor receives the respective CRF.

At any time other than the immediate index procedure during the study where complications prevent retention of the GORE® Septal Occluder (i.e., embolization or other event requiring device removal), the subject will be discontinued from further study follow-up. All adverse events will be collected and reported in compliance with this protocol through the point of device removal. The Investigator or designee will complete the Study Completion/Discontinuation Form documenting the subject's discontinuation from the clinical study.

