3.2 Study Endpoints

3.2.1 Primary Endpoint

The primary endpoint for the study is composite Clinical Success evaluated at 6 months post index procedure and is defined as satisfying all the following criteria:

1. Successful deployment and retention (at conclusion of index procedure) of a GORE® Septal Occluder
2. Freedom from:
 - any Serious Adverse Event (SAE) through 30 days post procedure
 - device events (post-procedure embolization, device removal, or other device reintervention) from completion of the implant procedure through the 6-month follow-up evaluation
3. A clinical residual defect status of completely occluded or clinically insignificant residual shunt at 6-month evaluation as determined by the Echo Core Lab (see Section 3.2.3)

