3.2.2 Secondary Endpoints

Technical Success: Successful deployment and retention of a GORE® Septal Occluder device at the conclusion of the index procedure.

CONFIDENTIAL INFORMATION

Procedure Success: Technical Success with the GORE® Septal Occluder and ≤ 2 mm residual shunt of the target ASD at conclusion of the index procedure.

Closure Success (Efficacy): Technical Success and measured residual defect status of occluded/trivial, evaluated at 6 months, 12 months, and 36 months post index procedure.

Safety: A calculation of the proportion of subjects experiencing one or more Serious Adverse Event(s) (SAE) in the first 30 days post index procedure and/or a device event (embolization, device removal, reintervention after completion of index procedure) through 6 months, 12 months, and 36 months post index procedure.

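### Section 5.5 requires withdrawal of a relocated subject with no suitable new physician, so late device events go uncollected even when the subject still consents and can be telephoned

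*Combined protocol and SAP*

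**What the plan says.** The rule is in Section 5.5: "The subject will be withdrawn if he/she relocates to another geographic area that requires a change of physician". The sentence goes on to a second condition, that the move "requires a change of physician and such suitable physician cannot be identified". Both must hold. When they do, the wording leaves the site no choice. Section 9.6 has adverse events reported from enrolment until completion or discontinuation, and no section provides for contact after withdrawal.

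Two endpoints depend on device events after the procedure:

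- The Safety endpoint (Section 3.2.2) counts embolization, removal and "reintervention after completion of index procedure) through 6 months, 12 months, and 36 months post index procedure".
- The primary endpoint (Section 3.2.1) requires freedom from such events "from completion of the implant procedure through the 6-month follow-up evaluation". It also requires no serious adverse event through 30 days and an acceptable core-lab echo reading at 6 months.

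The protocol already uses the telephone twice. Section 5.4.8 says: "At the 24 month interval subjects should be contacted and a telephone questionnaire CRF completed". The schedule in Section 5.2 marks adverse-event assessment at that contact, with no examination, ECG or imaging. For a failed implant, Section 5.4.6 says: "Subjects will be contacted by phone at 30 days for follow-up". At the 30-day, 6-, 12- and 36-month intervals, by contrast, "a TTE or TEE is required for all subjects with the GORE® Septal Occluder to evaluate defect closure status".

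**The concern.** The trigger for withdrawal is logistical. The subject has not refused contact, has not been lost and still carries the device. Observation stops because no physician was found, although part of what the study needs could be asked by telephone.

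The clearest case is a subject who moves after the 12-month visit. The next scheduled contact is the 24-month call, which needs no physician visit, yet the rule cancels it. Section 5.6 makes a telling comparison: a subject who misses a visit is declared lost only after three documented attempts at contact, whereas a relocated subject who answers the telephone is withdrawn.

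At stake is the completeness of device-event data at 12 and 36 months. For a move before 6 months, the study also never learns of a later event that would make the subject a primary-endpoint failure. Sections 5.4.8 and 5.5 themselves warn that the objectives suffer if many subjects are lost.

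**Working it through.** **1. The plan's own sample size.** Inputs from Sections 10.4 and 10.6.3: success 86.6% in both groups, 253 controls, 135 evaluable test subjects, margin 0.10, critical value 1.64 (one-sided 0.05).

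- Standard error = √[0.866 × 0.134 × (1/253 + 1/135)] = 0.0363
- Power = Φ(0.10/0.0363 − 1.645) = Φ(1.109) = 0.866, against a stated ≥0.86
- Enrolment = 135/0.90 = 150, as stated

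The design is reproduced.

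**2. What a call adds to the primary analysis.** Clinical Success needs the 6-month core-lab echo (Section 3.2.1). The per-protocol population needs evaluation completed through 6 months (Section 10.6.2). A call supplies neither, so the evaluable number stays at 135 and power at 0.866. Even if all 15 subjects in the 10% allowance were relocated subjects whose 6-month echo was also obtained, power would be Φ(0.10/0.0351 − 1.645) = 0.886. A call can establish a failure, because a removal or reintervention fails the composite whatever the echo shows. That matters for the intent-to-treat population, which includes all enrolled subjects.

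**3. What a call could supply, by interval** (Sections 5.2 and 5.4.8).

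| Interval | Planned contact | Obtainable by telephone | Still missing |
|---|---|---|---|
| 30 days, 6 months | Visit with echo | Adverse events; device events known to the subject | Echo, hence Clinical Success and Closure Success |
| 12 months | Visit with echo | Same | Echo, hence Closure Success |
| 24 months | Telephone questionnaire | Everything planned | Nothing |
| 36 months | Visit with echo | Adverse events; device events known to the subject | Echo, hence Closure Success |

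Fluoroscopy at 6 and 36 months, mandatory for the first 150 subjects (Section 5.4.8), would also be missing.

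**4. Size.** The documents give no rate for moves without a suitable physician. Take r = 2–6% over 36 months, purely as an assumption.

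- Subjects affected: 0.02 × 150 = 3 to 0.06 × 150 = 9; with 400 enrolled, 8 to 24.
- If moves are spread evenly, 6/36 = 1/6 fall before 6 months: 0.5–1.5 of 150, or 1.3–4 of 400.
- Mean follow-up lost per affected subject: 36/2 = 18 months.
- If device events are also spread evenly, and withdrawn subjects stay in the denominator as event-free, the share of 36-month events missed is r/2 = 1–3%.

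The last line rests on two further assumptions. No section fixes the Safety denominator, and if device events cluster soon after implantation the share missed is smaller.

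**The case against.** The strongest reply is that this is a retention preference, not an error. The rule contradicts nothing and threatens no planned test, and the 10% allowance was set for withdrawal and loss. That is fair. It limits the weight of the point but does not remove it, because the data are lost by a written rule that is easily changed.

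Several stronger readings are tempting, and the documents do not support them:

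- **That everyone who moves is withdrawn.** The second condition in Section 5.5 excludes this: a subject who finds a suitable physician stays in.
- **That a call is enough for device-event status.** For implanted subjects the protocol relies on the telephone only at 24 months, when no endpoint is evaluated; 6, 12 and 36 months are imaging visits. Removals and reinterventions would usually be known to the subject, but a silent event might not be. This limitation stands.
- **That the change would win back part of the 10% allowance or raise power.** Step 2 of the working shows that it does not.
- **That data are thrown away.** Nothing removes data gathered before withdrawal; later data are simply not collected.
- **That the administrative withdrawal date distorts results.** Section 5.5 also says: "The subject will be considered withdrawn once the Sponsor receives the respective CRF". But the primary analysis compares proportions (Section 10.6.3) and the secondary endpoints are descriptive (Section 10.6.4), so that date feeds no planned analysis.

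**Conclusion.** The point holds in a narrow form and is minor. For subjects who relocate and have no suitable physician, Section 5.5 makes withdrawal compulsory. Section 9.6 then ends adverse-event and device-event collection, with no remote alternative, although the protocol accepts a telephone contact at 24 months. What is lost is device-event information for the 12- and 36-month Safety endpoint and, for early movers, knowledge of primary-endpoint failures before 6 months.

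The size is unknown and probably modest. The 3–9 of 150, 8–24 of 400 and 1–3% figures illustrate an assumed relocation rate and are not estimates from the documents. The primary test keeps its power of 0.866 with or without the change.

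**What to change.** Replace the mandatory withdrawal in Section 5.5 with wording such as: a subject who relocates and for whom no suitable physician is found remains enrolled; adverse-event status and device-event status (embolization, removal, reintervention) are collected with the existing telephone questionnaire at each remaining interval; echo images obtained locally are uploaded to the core-lab portal where available; follow-up ends only if the subject withdraws consent or is lost under Section 5.6.

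Two details need attention. The questionnaire form is not in the documents, so check that it asks about each of the three device events. Section 5.7 ties completion to the 36-month visit, so state how a subject reached only by telephone at 36 months is classified. If the sponsor prefers to keep the rule, a sentence explaining why consenting, reachable subjects cannot be followed by telephone would suffice.

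The cost is amended protocol text and a few calls, using a form that already exists. Echo-based endpoints may still be missing for these subjects, and telephone ascertainment is less sensitive than an imaging visit, so telephone-only device-event status should be identified as such when the Safety endpoint is reported.
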